The Title of the study:

Nintendo Wii Virtual Reality Application In Older People With Alzheimer's Dementia

Date of the document:

September 26, 2017: Permission was obtained from the Ministry of Family and Social Policies.

December 12, 2017: The permission for the study was obtained from Karamanoğlu Mehmet Bey University Faculty of Health Sciences, Non-Invasive Clinical Research Ethics Committee.

August 15, 2017: The literature was scanned.

January 15 / April 30 2018: Data has been collected.

May 15, 2018: Statistical Analysis was performed.

January 18, 2020: Results were analyzed. Primary Completion Date

Author Information:

[name] PT^a, [name] PT, Assoc. Prof^{b*}

^a Hacettepe University, Faculty of Physical Therapy and Rehabilitation, [name]. [contact]

^b Kırıkkale University, Faculty of Health Sciences, Department of Physical Therapy and Rehabilitation, Kırıkkale, Turkey, TR71450. [contact]

ORCID Number: [name] - 0000-0002-7575-9762, [name] - 0000-0002-0059-5636

Corresponding Author:

[name], PT, ASSOC. PROF.

Department of Physiotherapy and Rehabilitation,
Kırıkkale University Faculty of Health Sciences

[contact]

e-mail: [contact]

Nintendo Wii Virtual Reality Application In Older People With Alzheimer's Dementia

Abstract

Purpose: This study was planned to investigate the effects of the Nintendo Wii virtual reality application on muscle strength and fall risk in individuals with AD.

Method: The study included a total of 32 volunteers between the ages of 65-80, with mild or moderate AD diagnosed. These individuals were divided into 2 groups as a training group and control group. The training group was trained with games from different categories such as balance and aerobic exercises with a Nintendo Wii virtual reality device 2 times a week for a period of 6 weeks, with 1 session lasting for 30 minutes. Mini-Mental State Test, Knee Extension Muscle Strength, Timed Up and Go Test, Tinetti Falls Efficacy Scale results of individuals were recorded in the evaluation.

Results: The mean age of the control group was 73.13 ± 3.54 years, and the mean age of the training group was 73.75 ± 5.16 years. In the statistical analysis between groups, the Mini-Mental State Test values were found to be statistically significant in favor of the training group ($p=0.049$). In the intra-group statistical analysis, there was a significant difference in all tests in the training group after the training, while no significant difference was found in the control group.

Conclusions: It was found out that the virtual reality application in individuals with Alzheimer's dementia increased muscle strength and decreased the fall risk. As a result, supporting the physiotherapy and rehabilitation programs with technological developments and virtual reality applications will increase the success of the treatment.

Keywords: Alzheimer's Dementia; Muscle strength; Fall; Virtual reality

Study Procedure and Protocol

The study included a total of 32 volunteers between the ages of 65-80, who stayed in Karaman Ahmet Mete Nursing Home, Elderly Care and Rehabilitation Center, with mild or moderate Alzheimer's dementia diagnosed by a neurologist. There were 90 older people in Karaman Ahmet Mete Nursing Home, Elderly Care and Rehabilitation Center. Power analysis was performed to determine the size of the sample to be included in the study. As a result of the power analysis, assuming that the effect size to be obtained between the two groups will be large ($d = 0.9$), when at least 32 individuals (at least 16 individuals per group) were included in the study, it was calculated that 80% power could be obtained at 95% confidence level (with 0.05 error margin). As a result of the power analysis, it was calculated that at least 16 individuals could be included in each group (at least 32 individuals in total). 20% risk rate was determined for the individuals who could leave the study, 3 individuals were added to each group, and the study was organized with 19 individuals in each group. However, these people were excluded from the study as 4 people were not meeting inclusion criteria, 2 people were declined to participate, and therefore the study was completed with 32 individuals (Figure 1). The study included volunteers between the ages of 65-80 with mild or moderate AD diagnosis, who did not have any difficulty or problems in communicating, who did not have any neurological diseases that disrupt balance and coordination such as a cerebrovascular event, Parkinson's disease, Multiple Sclerosis, and neurological disorder, who obtained a score of 18 - 24 points in the Mini-Mental State Test (MMST) were included in the study. Patients diagnosed with rapidly progressing dementia (infection, vascular, hematologic diseases), those who could not be contacted during the follow-up period or who did not participate in the training session, those who experienced cardiac and cerebrovascular events, endocrine disorders, fluid-electrolyte imbalance and infection, those with malignancy and those who received chemotherapy and radiotherapy that causes malignancy, delirium or depression and malignant sensory loss (those with the Semmes-Weinstein monofilament thickness of 4.56 and above), and those with a lower or upper extremity amputation at any level were excluded from the study.

Among the 38 individuals with AD diagnosis, 1 individual was not included in the study after the first evaluation due to the MMST score lower than 18, 3 individuals were not included in the study due to the hearing and communication problems, and 2 individuals were not included because they did not want to start the study. The first evaluation of the patients was

performed before randomization. 32 individuals suitable for the criteria were included in the study (Figure 1). Randomization was performed by the sealed-envelope method. According to this method, 4 females and 12 males were determined to be in the control group, while 5 females and 11 males were determined to be in the training group.

The evaluation was completed before the intervention. The same evaluation was conducted after 6 weeks. The physiotherapist with more than 5 years of experience conducted all the evaluations. Exercise training was given by another 2-year experienced physiotherapist. The training group was trained with games from different categories such as balance and aerobic exercises with a Nintendo Wii virtual reality device 2 times a week for a period of 6 weeks, with 1 session lasting for 30 minutes, and each patient was trained with the same games. In the control group, no application was performed during this period, and routine medical treatments were continued. The training group was evaluated before and after the training, while the control group was re-evaluated at the end of the 6th week after the first evaluation. After the study was completed, the volunteers from the control group were also given training.

In order to determine the sociodemographic characteristics of individuals, the case report form included questions about name and surname, age, height, weight, body mass index, dominant side, smoking, alcohol use, previous occupation, marital status, educational status, income level, number of children, social security, special healthcare needs, number of falls in the last year, vision problems, personal history, family history, medicines used, surgeries undergone, and use of a walking stick.

Their cognitive status was evaluated by the MMST. According to the MMST, 24-30 points were considered as normal cognitive levels, 18-23 points were considered as mild cognitive disorders, and 0-17 points were considered as severe cognitive disorders.

Muscle strength was evaluated by the knee extension strength. The knee extension strength was measured by a hand-held muscle strength dynamometer (Baseline Evaluation System, New York). The knee extension strength measurement was preferred in this study because it is a measurement that gives information about general lower extremity muscle strength. The knee extension strength was evaluated in the sitting position with the hip and knee joint at 90° flexion. The patient was asked to arrange his/her leg, the force was applied over the ankle, and the patient was asked to resist this force and keep his/her position. This measurement was repeated 3 times bilaterally, and the arithmetic mean of the values was taken. This

measurement was performed twice as the first and last evaluation, and the results were recorded in kg-force [24].

The fall was evaluated with the Tinetti Falls Efficacy Scale (TFES), and this scale is a 10-item scale. These items include bathing, reaching out to shelves, walking inside the house, preparing food, going to bed and getting out of bed, answering the door, sitting on the chair and getting up from the chair, getting dressed and undressed, personal care, going to the toilet and leaving the toilet. The question of “How much do you feel confident while doing the above activities?” was asked to state a point between 1 and 10. 1 means very high confidence, and 10 means no confidence. A score between 0 and 100 is obtained in total. If the total score is more than 70 points, there is fear of falling.

[figure not shown]
The Timed Up and Go Test (TUG) is a test that assesses the fall risk, mobility and physical performance in older people. A chair and a stopwatch are required to perform the test. The test is carried out with the patient's usual shoes, and the patient is told that he/she can use walking aids if needed. This test was performed by giving the command to the individual to get up from the chair without arm support while sitting on the chair, to walk in a predetermined 3-meter area and return, and to sit again on the chair without arm support (Image 3.1). The result was recorded in seconds (sec). If the older people completes this test in a longer time than 12 seconds, there is a fall risk.

Each part of Nintendo Wii was introduced to the individuals in the training group in the first session and games were played with the support of a physiotherapist. How to play the selected games and their objectives were explained and taught to each individual by the physiotherapist in practice. The patient was supported with verbal and physical feedback when it was noticed that the patient made wrong movements during the games played in later sessions. Games that require serious strength, balance, and coordination such as Bird's eye Bull's eye, Obstacle Course, Balance Bubble, etc. were considered as a difficult activity for the patient and were not used in this study.

The difficulty of the games was set to the simplest level for each patient. Their difficulty level was increased as the patients became successful. The difficulty of the games was increased according to the classification determined by the Nintendo Wii device. The duration of each game was different, and the games were played until the end of their times. All games were played by the patients under the same conditions, in the same environment, at the same temperature and at the same time in each session.

The permission for the study was obtained from Karamanoğlu Mehmet Bey University Faculty of Health Sciences, Non-Invasive Clinical Research Ethics Committee. Voluntary consent forms were signed by both individuals with AD and caregivers of these individuals.

CONSORT 2010 Flow Diagram

Statistical Analysis Plan

The data were analyzed using the SPSS 24.0 packaged software. Continuous variables were presented as mean \pm standard deviation, median (minimum and maximum values), while categorical variables as number and percentage. The suitability of the data for normal distribution was examined by the Shapiro-Wilk test. The significance test of the difference between the two means was used in comparing the independent group differences when the parametric test assumptions were provided, and the Mann-Whitney U test was used in comparing the independent group differences when the parametric test assumptions were not provided. The significance test of the difference between the two pairs was used in comparing the dependent group differences when the parametric test assumptions were provided, and the Wilcoxon two-pPaired sample test was used when the parametric test assumptions were not provided. Differences between categorical variables were analyzed by chi-square analysis. In all analyses, $p<0.05$ was accepted as statistically significant.

Results

The mean age of the individuals was 73.13 ± 3.54 years, and the mean age of the training group was 73.75 ± 5.16 years. No statistically significant difference was found between the groups in terms of age, gender, height, weight, body mass index, occupation, marital status, education level, income level, number of children, and social security ($p>0.05$).

Upon examining the MMST values, the difference between the 2 groups was not statistically significant ($p>0.05$). In the post-training measurements, the values of the training group were significantly higher compared to the control group ($p<0.05$). When the changes in the groups before and after the training were examined, no statistically significant change was observed in the control group, whereas the values of the training group were significantly higher after the treatment ($p<0.05$).

When the right and left knee extension muscle strength values of individuals with AD were examined, the difference between the 2 groups was not statistically significant before and after the training ($p>0.05$). When the changes of the groups before and after the training were examined, there was no significant change in the control group, whereas the values of the training group were significantly higher after the training ($p<0.05$).

When the TFES values were examined, no difference was found between the 2 groups before and after the training ($p>0.05$). When the changes of the groups before and after the training were examined, there was no significant change in the control group ($p>0.05$), whereas the values of the training group were significantly lower after the training ($p<0.05$).

When the TUG test values were examined, there was no difference between the 2 groups before and after the training ($p>0.05$). When the changes of the groups before and after the training were examined, there was no significant change in the control group ($p>0.05$), whereas the values of the training group were significantly lower after the training ($p<0.05$).

Conclusion

Along with cognitive functions, losses in motor functions such as muscle strength, balance, coordination, and walking occur in individuals with AD. A good physiotherapy and rehabilitation program is required to prevent and treat these problems. The virtual reality environment is a computer-generated three-dimensional simulation of a real-world situation in which the user can sense and control this simulation environment sensorially by means of special devices. In conclusion, the support of physiotherapy and rehabilitation programs with technological developments and virtual reality applications will increase the success of treatment especially for muscle strength, walking speed, reduction of fall risk and cognitive functions. This training may work as well, and that the results indicate that it may reduce the risk of falls.

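### The only significant between-group result, MMST at p=0.049, is one of five unadjusted tests with no primary outcome and cannot support listing cognition among the areas of benefit

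*Combined protocol and SAP*

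**What the plan says.** The Abstract states the purpose as the "effects of the Nintendo Wii virtual reality application on muscle strength and fall risk in individuals with AD". The MMST is among the recorded measures, but cognition is not in the purpose. The power analysis in Study Procedure and Protocol assumes d = 0.9 without tying it to an outcome.

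The Statistical Analysis Plan gives one decision rule: "In all analyses, $p<0.05$ was accepted as statistically significant". No section names a primary outcome, an order of testing or a correction for several tests.

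The Results then report between-group comparisons after training:

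- MMST: "In the post-training measurements, the values of the training group were significantly higher compared to the control group ($p<0.05".
- Right and left knee extension strength: "the difference between the 2 groups was not statistically significant before and after the training ($p>0.05".
- Tinetti Falls Efficacy Scale (TFES): "When the TFES values were examined, no difference was found between the 2 groups before and after the training ($p>0.05".
- Timed Up and Go (TUG): "When the TUG test values were examined, there was no difference between the 2 groups before and after the training ($p>0.05".

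The Abstract's sentence on between-group analysis gives only the first of these, as "the Mini-Mental State Test values were found to be statistically significant in favor of the training group ($p=0.049", without a time point. The Conclusion says, without hedging, that adding virtual reality to rehabilitation will make treatment more successful in four named areas, of which cognition is one. The softer sentence that closes the section opens in general terms and then specifies falls.

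**The concern.** When five outcomes are each tested at 0.05 and none is designated in advance, one result just under the threshold is weak evidence. Here the one significant result is at 0.049, on an outcome that the study was not set up to address. The Abstract shows it without the four between-group tests that did not reach significance, so a reader cannot see that it was one of five. The Conclusion then names cognition as an area of expected benefit. This between-group test is the only randomised comparison that could support that statement.

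**Working it through.** **Inputs.** p = 0.049 for MMST (Abstract, Results); p>0.05 for right knee, left knee, TFES and TUG after training (Results); threshold 0.05 (Statistical Analysis Plan); 16 per group (Study Procedure and Protocol). The 0.049 cannot be recomputed, because the documents give no MMST group means or standard deviations and do not say which test was used. It is taken as stated.

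**Step 1: which comparison is 0.049?** The Results give two between-group statements for MMST. The first is non-significant and, from its place before the post-training sentence, refers to baseline. The second is post-training with p<0.05. Since 0.049 < 0.05, only the second fits.

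**Step 2: adjusted p-value over the five reported tests.** MMST has the smallest p-value.

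- Bonferroni, and Holm's first step: 5 × 0.049 = 0.245. The first-step threshold is 0.05/5 = 0.01.
- Sidak: 1 − (1 − 0.049)^5 = 1 − 0.951^5 = 0.222.
- Knees counted as one outcome, Bonferroni: 4 × 0.049 = 0.196.
- Hochberg, Hommel and Benjamini-Hochberg: these depend on the other four p-values, which are known only to exceed 0.05. In the most favourable case, with all four at 0.0501, the adjusted MMST p is 0.0501. Higher values raise it.

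**Step 3: does correlation between outcomes rescue it?** The documents give no correlations, so a range is assumed. The figures come from a simulation under the null with five equally correlated normal outcomes, 16 per arm, two-sided tests and 100,000 runs. The adjusted p is the chance that the smallest of the five p-values is 0.049 or less.

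| Assumed correlation | t-tests | Mann-Whitney tests |
|---|---|---|
| 0.3 | 0.207 | 0.201 |
| 0.5 | 0.181 | 0.175 |
| 0.7 | 0.150 | 0.148 |
| 0.9 | 0.101 | 0.102 |

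None is below 0.05.

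**Step 4: chance of at least one false significant result among five tests at 0.05.** If independent: 1 − 0.95^5 = 0.226. In the same simulation with t-tests: 0.211, 0.184, 0.153 and 0.103 at correlations 0.3, 0.5, 0.7 and 0.9.

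**Step 5: leave MMST out as exploratory.** The other four tests are all p>0.05 before any adjustment, so no between-group result is significant in that family either.

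**The case against.** **Little turns on it.** The Abstract's own conclusion names muscle strength and fall risk, not cognition, and the between-group tests for those outcomes were non-significant already. This stands and sets the reach of the point. A reader might infer that multiplicity is what undermines the strength and fall-risk conclusions. It is not: correction changes none of those tests. That those conclusions rest on within-group changes is a separate matter.

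**The family of five is a choice, and 0.049 fails almost any correction.** Both are true. With only two tests, Bonferroni already gives 2 × 0.049 = 0.098. The Results also report within-group tests in both arms, which the family of five leaves out. Adding them would not help MMST: the other four between-group p-values are larger than 0.049, so Holm's multiplier stays at 5 or more and the adjusted p at 0.245 or more.

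**A small study with no declared confirmatory endpoint need not adjust.** This is defensible, and it is why an adjusted p-value is not demanded. MMST should then be labelled exploratory, which the documents do not do. The 0.049 would stand unadjusted had MMST been prespecified as the sole primary or first-tested outcome, but nothing says so.

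**The MMST also rose within the training group.** The Results say "no statistically significant change was observed in the control group, whereas the values of the training group were significantly higher after the treatment ($p<0.05". A significant change in one arm beside a non-significant change in the other is not a comparison between arms, and these tests are unadjusted too.

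**The Conclusion is a loose recommendation.** It does not cite the MMST result, and the section ends in softer terms. Even so, the sentence naming cognition is unhedged.

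**Stronger readings that the documents do not support.** A reader might infer that training has no effect on cognition; failing a correction with 16 per group does not show that. A reader might also suspect that MMST was added after the results were seen, but it is described among the measures. Finally, d = 0.9 with 16 per group gives 80% power only one-sided, which might suggest that 0.049 is one-sided. The sidedness of the tests is not stated, so that cannot be concluded.

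**Conclusion.** The point holds in a limited form. MMST at p=0.049 is the only significant result among five reported post-training between-group tests. It was obtained under an unadjusted rule with no designated primary outcome, and it concerns an outcome outside the stated purpose. It becomes 0.245 under Holm or Bonferroni over five tests and 0.196 with the knees counted once. It stays above 0.05 under every standard method tried and across assumed correlations of 0.3 to 0.9. It does not support naming cognition as an area where treatment success will improve.

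This rests on taking 0.049 as reported and on linking it to the post-training test, the only reported MMST between-group comparison that it fits. The simulated figures also rest on equally correlated normal outcomes. What changes is the label on p=0.049 and the mention of cognition in the Conclusion. The change should be made, but it is a reporting correction that needs no new analysis.

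**What to change.** - In the Abstract, give the time point for p=0.049.
- Describe MMST there and in the Results as an unadjusted, exploratory finding: one significant test out of five, with no multiplicity control planned.
- Report the four non-significant between-group results beside it in the Abstract.
- In the Conclusion, remove cognition from the list of areas of benefit, or qualify it as an unadjusted exploratory finding.

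Optionally, give the Holm value (0.245 over five tests) as a post hoc sensitivity figure, disclosed as chosen after the May 2018 analysis. A full column of adjusted p-values is not needed.

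The cost is a few wording edits, with no new data and no new outcome test. The downside is that the marginal MMST claim is lost as a stated benefit. Keeping the unadjusted p-value in view limits that loss.

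### The claim that training increased muscle strength and lowered fall risk rests on within-arm tests; the reported between-group comparisons do not show it

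*Combined protocol and SAP*

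**What the plan says.** The Abstract gives the aim: "This study was planned to investigate the effects of the Nintendo Wii virtual reality application on muscle strength and fall risk". The sample size in Study Procedure and Protocol is built on a large effect (d = 0.9) between the two groups, with 16 per group.

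The Statistical Analysis Plan lists two-sample tests (parametric or Mann-Whitney) and paired tests (parametric or Wilcoxon). It does not say which of them supports a claim of efficacy.

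The Results report these between-group comparisons, all at p>0.05:
- Right and left knee extension strength: "the difference between the 2 groups was not statistically significant before and after the training".
- TFES: "When the TFES values were examined, no difference was found between the 2 groups before and after the training".
- TUG: "When the TUG test values were examined, there was no difference between the 2 groups before and after the training".

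For the same outcomes, the paired tests were significant in the training arm and not in the control arm. The Abstract summarises this as "a significant difference in all tests in the training group after the training, while no significant difference was found in the control group".

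The Abstract then concludes: "It was found out that the virtual reality application in individuals with Alzheimer's dementia increased muscle strength and decreased the fall risk". The closing Conclusion says that such applications "will increase the success of treatment especially for muscle strength, walking speed, reduction of fall risk and cognitive functions", and its last sentence is softer: "the results indicate that it may reduce the risk of falls".

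**The concern.** A significant change in one arm and a non-significant change in the other is not evidence that the arms differ. The difference between the two changes has its own standard error, and it can be far from significant when one p-value falls just below 0.05 and the other above it. Change in the training arm alone also mixes any training effect with whatever would have happened anyway, such as repeat testing or natural variation. The control arm exists to remove that part, and a separate paired test in each arm does not use it.

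The conclusion on both stated objectives is therefore presented as shown, although the randomised comparison, as reported, did not show it. The Abstract's Results mention only one between-group result, the Mini-Mental State Test (p=0.049), and leave out the four non-significant ones on strength and fall risk. A reader of the Abstract alone cannot see the gap. The Mini-Mental result is not part of this point.

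**Working it through.** **Inputs.** From the documents: 16 per arm, planned d = 0.9, 5% significance level. No outcome means, SDs or exact p-values are given for strength, TFES or TUG, so the steps below are illustrations. They use t-tests; the documents do not say whether t or rank tests were used for each outcome, so the figures are approximate.

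**The plan's own figure.** A two-sample t-test with d = 0.9 and 16 per group has 80.0% power one-sided and 69.3% two-sided. The stated size thus reproduces as a one-sided calculation; the documents do not state sidedness. It is a calculation for a between-group contrast.

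**Step 1: what a difference in change requires.** Assume the same SD of change in both arms. Then

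t(between) = [t(training) − t(control)] / √2, on 30 df.

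The critical value is 2.042, so the gap must be at least 2.042 × √2 = 2.89. If the control change is exactly zero, t(training) itself must reach 2.89 on 15 df, which is p = 0.011. A paired test alone needs only t = 2.13.

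Examples, with t(training) = 2.3 (p = 0.036):

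| Control change | t(control) | Control p | t(between) | Between-arm p |
|---|---|---|---|---|
| Improves | +1.0 | 0.33 | 1.3/√2 = 0.92 | 0.37 |
| None | 0 | 1.00 | 2.3/√2 = 1.63 | 0.11 |
| Worsens | −1.0 | 0.33 | 3.3/√2 = 2.33 | 0.027 |

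All three rows show the reported pattern (training significant, control not), yet the between-arm answer runs from clearly non-significant to significant. The documents do not give the direction of the control change, so the pattern does not settle the question.

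**Step 2: how often the pattern arises with no treatment effect.** Assume the same true standardised change (dz) in both arms. For one outcome the rate is

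P(training p<0.05 in the favourable direction) × P(control p≥0.05),

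from the noncentral t distribution with 15 df:

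| Assumed dz | 0 | 0.1 | 0.2 | 0.3 | 0.5 |
|---|---|---|---|---|---|
| Rate, one outcome | 2.4% | 5.3% | 10% | 16% | 25% |

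For all four outcomes at once, which is what was reported, simulation (200,000 replicates) gives much lower rates:

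| Assumed dz | Correlation 0 | 0.5 | 0.8 |
|---|---|---|---|
| 0 | 0.0% | 0.05% | 0.4% |
| 0.3 | 0.1% | 1.7% | 5.2% |
| 0.5 | 0.4% | 3.5% | 9.3% |

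The dz values and the correlations between outcomes are assumptions.

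**Step 3: what the between-group tests could show.** The unadjusted 95% CI half-width is 2.042 × √(2/16) = 0.72 SD. For ANCOVA, with baseline to week-6 correlation r and ignoring chance baseline imbalance, it is 2.045 × √(2/16) × √(1 − r²):

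| Assumed r | 0.5 | 0.7 | 0.9 |
|---|---|---|---|
| Half-width (SD) | 0.63 | 0.52 | 0.32 |

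The reported comparisons of raw values are imprecise, and an adjusted analysis could give a different answer.

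**The case against.** The strongest reply is that all four outcomes point the same way. With no treatment effect that is uncommon unless the outcomes are highly correlated (Step 2), and the documents give no evidence of a common improvement in both arms. This stands as a suggestive signal, and the single-outcome rates should not carry the argument. But the four outcomes come from the same 32 people, and a consistent pattern of paired tests still supplies no between-arm estimate or interval.

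Second, if controls worsened, the change could differ significantly between arms. That is correct, as the last row of the Step 1 table shows. It means the claim might be supportable; it does not mean the documents support it.

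Third, the trial was small. That is a reason to avoid saying there is no effect, but low power does not turn a non-significant comparison into a positive finding.

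Fourth, the Results state the non-significant comparisons openly, and the last sentence of the Conclusion is hedged. Both are true, and nothing is concealed there. The hedge does not reach the Abstract, and the sentence before it is not hedged.

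Fifth, the wording of the Statistical Analysis Plan on independent-group differences could be read to include differences in change. Even so, the Results describe only comparisons before and after training. No outcome tables are in the text, so the point is limited to what is reported.

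Finally, four post hoc tests bring multiplicity: under independence the chance of at least one false positive is 1 − 0.95⁴ = 18.5%. Reporting all four with a post hoc label limits selective use but does not remove this, so one isolated p<0.05 should not restore the headline.

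**Conclusion.** The concern holds. As reported, no between-group test supports the Abstract's conclusion on muscle strength or fall risk: all four relevant comparisons after training are p>0.05. The conclusion depends on comparing significance within arms, which does not test the treatment effect and departs from the between-group contrast on which the trial was sized.

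This follows from the text alone and needs no assumption. How far the inference could mislead depends on assumed changes, equal SDs of change and t-tests, and cannot be fixed from the documents. The correct statement is that an effect on knee strength, TUG or TFES was not demonstrated. With a half-width of 0.72 SD and 69% two-sided power at d = 0.9, absence of an effect has not been shown either. The Abstract sentence must be corrected.

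**What to change.** 1. For right knee strength, left knee strength, TFES and TUG, report the training-minus-control difference at week 6 with its 95% CI, adjusted for that outcome's baseline value (ANCOVA). Add a rank-based version where residuals are clearly non-normal.
2. Report all four whatever the result, and label them post hoc, since the document dates the statistical analysis to May 2018.
3. Base efficacy statements only on these contrasts, and present within-arm changes as description.
4. Reword the Abstract and the Conclusion. For example: the between-group comparisons did not demonstrate an effect of training on knee extension strength, TUG or TFES; with 16 participants per group, an effect cannot be ruled out. State in the Abstract's Results that these comparisons were non-significant. Change this wording only if the adjusted analyses show otherwise.

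The cost is four regressions on baseline and week-6 values already collected, and a rewritten conclusion. The price to the authors is the post hoc label and probably a less favourable headline. If the regressions are not run, the rewording in item 4 is still needed.
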